8.2.7. Days of Invasive Mechanical Ventilation/ECMO

Duration of Invasive Mechanical Ventilation/ECMO use will be summarized in a table using medians and quartiles by treatment arm. Analyses will be performed in the mITT and As Treated populations. Bee swarm plots of Invasive Mechanical Ventilation/ECMO days by treatment arm will be generated, where subjects whose days are imputed to the maximum of 28 days due to death are grouped separately from subjects who do not die.

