Analysis Population	Oxygen Use	Statistic	Treatment Group				
			Interferon beta-1a + RDV	Placebo + RDV			
On Oxygen at Baseline (N = x)							
mITT Population	Days on Oxygen (Including imputations for subjects who died) ^a	N	x	x			
		Q1	x.x	x.x			
		Median	x.x	x.x			
		Q3	x.x	x.x			
		Difference in Medians (95% CI)	x.x (x.x, x.x)				
	Days of Oxygen (Among subjects who did not die)	N	x	x			
		Q1	x.x	x.x			
		Median	x.x	x.x			
		Q3	x.x	x.x			
		Difference in Medians (95% CI)	x.x (x.x, x.x)				
Not on Oxygen at Baseline (N = x)							
	New Oxygen Use	N	x	x			
		n	x	x			
		Incidence Rate	x.x	x.x			
		Incidence Rate 95% CI	x.x, x.x	x.x, x.x			
		Difference in Rates (95% CI)	x.x (x.x, x.x)				
	Days on Oxygen (Including imputations for subjects who died) ^a	N	x	x			
		Q1	x.x	x.x			
		Median	x.x	x.x			
		Q3	x.x	x.x			
		Difference in Medians (95% CI)	x.x (x.x, x.x)				
	Days of Oxygen (Among subjects who did not die)	N	x	x			
		Q1	x.x	x.x			
		Median	x.x	x.x			
		Q3	x.x	x.x			
		Difference in Medians (95% CI)	x.x (x.x, x.x)				
Repeat for As Treated Population.							
N = Number of subjects in the specified analysis population and oxygen use category.							
Q1 and Q3 are the first and third quartiles, respectively.							
Refer to Section 11.4.2.2 of the Clinical Study Report for details regarding imputations.							
^a Subjects who died were imputed as 28 days.							

Programming Note: For the “Days on Oxygen” statistics within the “Not on Oxygen at Baseline” subgroup, only summarize days for subjects who reported new use.

Tables with similar format:

Table 34: **Oxygen Use by Treatment Group – Baseline Ordinal Score of 6**

Table 35: **Oxygen Use by Treatment Group and Duration of Symptoms at Baseline – Baseline Ordinal Score of 4 or 5**

Table 36: **Non-invasive Ventilation/High-Flow Oxygen Use by Treatment Group – Baseline Ordinal Score of 4 or 5**

Table 37: **Non-invasive Ventilation/High-Flow Oxygen Use by Treatment Group – Baseline Ordinal Score of 6**

Table 38: **Non-invasive Ventilation/High-Flow Oxygen Use by Treatment Group and Duration of Symptoms at Baseline – Baseline Ordinal Score of 4 or 5**

Table 39: **Ventilation/ECMO Use by Treatment Group – Baseline Ordinal Score of 4 or 5**

Table 40: **Ventilation/ECMO Use by Treatment Group – Baseline Ordinal Score of 6**

Table 41: **Ventilation/ECMO Use by Treatment Group and Duration of Symptoms at Baseline – Baseline Ordinal Score of 4 or 5**

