Programming notes for Table 35, Table 38, and Table 41:

“Analysis Population” will be replaced by “Duration of Symptoms at Baseline” column. The tables will consider the duration above/below median subgroup. Summaries will only be generated for mITT population.

Programming notes for Table 39, Table 40, Table 41:

The “On Ventilation/ECMO at Baseline” section of the table will not be generated.

Programming notes for Table 34 and Table 37:

The “New Use” section of the table will not be generated.

Programming notes for Table 38:

The “On Non-Invasive Ventilation/High-Flow Oxygen at Baseline” section of the table will not be generated.

Table 42: Hospitalization by Treatment Group – Baseline Ordinal Score of 4 or 5

Analysis Population	Summary	Statistic	Treatment Group				
			Interferon beta-1a + RDV	Placebo + RDV			
mITT Population	Days of Hospitalization (including imputation for subjects who died) ^a	N	x	x			
		Q1	x.x	x.x			
		Median	x.x	x.x			
		Q3	x.x	x.x			
		Difference in Medians (95% CI)	x.x (x.x, x.x)				
	Days of Hospitalization (among subjects who did not die)	N	x	x			
		Q1	x	x			
		Median	x	x			
		Q3	x.x, x.x	x.x, x.x			
		Difference in Medians (95% CI)	x.x (x.x, x.x)				
	Readmittance	N	x	x			
		n	x	x			
		Percentage	x	x			
		Percentage 95% CI	x.x, x.x	x.x, x.x			
		Difference in Rates (95% CI)	x.x (x.x, x.x)				
Continue for As Treated Population....							
N = Number of subjects in the specified analysis population.							
Q1 and Q3 are the first and third quartiles, respectively.							
Denominator of readmittance percentages is the number of subjects in the specific analysis population.							
^a Subjects who died were imputed as 28 days.							

Tables with similar format:

Table 43: Hospitalization by Treatment Group – Baseline Ordinal Score of 6**Table 44: Hospitalization by Treatment Group and Duration of Symptoms at Baseline – Baseline Ordinal Score of 4 or 5**

Programming Note for Table 41: “Analysis Population” will be replaced by “Duration of Symptoms at Baseline” column. The table will consider the duration above/below median subgroup. Summaries will only be generated for mITT population

Table 45: Summary Statistics of Laboratory Efficacy Results by Study Visit Day, and Treatment Group – mITT Population, Baseline Ordinal Score of 4 or 5

Laboratory Parameter	Study Visit Day	Treatment Group	Absolute					Change from Baseline				
			N	Mean	95% CI	Median	Min, Max	N	Mean	95% CI	Median	Min, Max

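### Days of new oxygen, non-invasive ventilation/high-flow or ventilation/ECMO are contrasted between arms only among patients who started that support after randomization

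*SAP*

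**What the plan says.** SAP 3.3.6 to 3.3.8 define days of each type of support as a count of days at the relevant ordinal scores, so every subject has a value and it can be 0. SAP 8.2.3, 8.2.5 and 8.2.7 call for summaries by arm in the mITT and As Treated populations. For ventilation the wording is "Duration of Invasive Mechanical Ventilation/ECMO use will be summarized in a table using medians and quartiles by treatment arm". None of these sections limits the summary to users.

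The limit appears in SAP Appendix 1. Table 33 has one block for patients on oxygen at baseline and one for those not on it. In the second block the note is to "only summarize days for subjects who reported new use". That block shows a between-arm difference in medians with a 95% CI twice: once with deaths included (footnote: "Subjects who died were imputed as 28 days") and once among survivors.

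Tables 34 to 41 are listed as having a similar format, including "Non-invasive Ventilation/High-Flow Oxygen Use by Treatment Group – Baseline Ordinal Score of 4 or 5" (Table 36) and "Ventilation/ECMO Use by Treatment Group – Baseline Ordinal Score of 4 or 5" (Table 39). For Tables 39 to 41, the section labelled "On Ventilation/ECMO at Baseline" is not generated.

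SAP 8.2.4, 8.2.6 and 8.2.8 identify new use by a score recorded after randomization: at least 5 for oxygen, 6 for non-invasive ventilation/high-flow, and 7 for ventilation/ECMO.

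**The concern.** Restricting a between-arm contrast to users selects on an outcome of treatment. If one arm avoids short episodes, its remaining users are the sicker ones and their median is longer. If one arm adds short episodes, its median is shorter. In both cases the duration row can point away from the total burden of support. The survivors-only row adds a second post-randomization condition.

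At stake is the reading of secondary endpoints. SAP 3.1 lists support use up to Day 29 separately from the incidence and duration of new use. The shell serves the second objective. For ventilation/ECMO, and for non-invasive ventilation/high-flow in scores 4 and 5, it gives the first no tabulated all-patient contrast.

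**Working it through.** The documents give no sample size, power or expected value for the duration endpoints, so there is no planned figure to reproduce. The check has two parts.

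**1. Which tables are reached**

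- Table 33, and Table 35 by layout: the block for patients not on oxygen at baseline is users-only. The on-oxygen block is not.
- Tables 36 and 38: nobody with baseline score 4 or 5 is on non-invasive ventilation/high-flow, so only the new-use block has patients.
- Tables 39 to 41: the at-baseline block is dropped, so only the new-use block remains.
- Tables 34 and 37 (baseline score 6): the new-use section is not generated, so they are unaffected.

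**2. Direction and size, under assumptions that are not in the documents**

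Let p be the incidence of new support in the control arm and s the share of short episodes among users. Short episodes last 1 to 6 days (uniform, mean 3.5) and long ones 8 to 28 days (uniform, mean 18). The drug prevents a fraction f of short episodes and leaves long ones alone. There are no deaths in this illustration.

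- Incidence: control p; treated p × [s(1 − f) + (1 − s)]
- Mean days, all patients: control p × [3.5s + 18(1 − s)]; treated p × [3.5s(1 − f) + 18(1 − s)]
- Users-only median: depends on s and f, not on p

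For p = 40%, s = 60%, f = 50%:

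- Incidence: 40% v 0.40 × (0.30 + 0.40) = 28%.
- Mean days: 0.40 × (2.1 + 7.2) = 3.72 v 0.40 × (1.05 + 7.2) = 3.30.
- Control users' median: 60% × 5/6 = 50%, so it sits between 5 and 6 days.
- Treated users' median: short share 0.30/0.70 = 42.9%. The other 57.1% spreads over 21 values at 2.72% each. A further 7.1% is needed, which falls on the third value, 10 days.

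Other cells at p = 40%:

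| s | f | Incidence | Users-only median | Mean days, all |
|---|---|---|---|---|
| 50% | 75% | 40% v 25% | 7 v 15 | 4.30 v 3.775 |
| 60% | 50% | 40% v 28% | 5 to 6 v 10 | 3.72 v 3.30 |
| 70% | 25% | 40% v 33% | 5 v 5 | 3.14 v 2.895 |

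Over the whole grid (p 20% or 40%, s 50% to 70%, f 25% to 75%), the users-only median moves by 0 to about 8 days against the drug. The all-patient mean always falls, by about 0.1 to 0.7 days. The all-patient median is 0 in both arms throughout.

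Swapping the arms gives the opposite error. In the middle row, a drug that raised incidence from 28% to 40% by adding short episodes would show a users-only median falling from 10 days to between 5 and 6, while mean days rose from 3.30 to 3.72.

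In 2000 simulated trials of the middle row, with an assumed 150 patients per arm not on the support at baseline, the users-only median was longer on the drug in 91%. A rank test among users (used only as a gauge; the shell plans none) was nominally significant toward harm in 31%, against about 2% with no drug effect. With 75 per arm the figures were 82% and 17%.

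**The case against.** Much of the case on the other side stands.

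- The rows just above the duration rows give the incidence of new use and a difference in rates with CI, among everyone not on that support at baseline. In the middle row above, a reader would see 40% v 28%.
- SAP 9.4 plans time to death or progression to ventilation in all randomized patients (Tables 83, 86 and 87), which does not condition on use.
- Duration of new use is a stated objective and exists only for users, so describing it among users is faithful to that objective.
- The size is assumed. With episodes of exactly 6 or 16 days and all short ones averted, the users-only medians are 16 v 16 if 40% are short, 11 v 16 if half are, and 6 v 16 if 60% are. The protocol's control scenarios put only 1% to 3% on ventilation/ECMO at Day 15. That is a prevalence rather than an incidence, but it suggests that ventilated users may be few.
- Counting deaths as 28 days makes an all-patient measure partly a mortality measure, and a rank test on mostly zeros leans on incidence.

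These points limit the consequence and the claim of size. They do not make the printed difference and its CI a randomized comparison. The planned bee swarm plots of days in the mITT population do not settle it either, because the text does not say whether non-users appear at 0.

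**Conclusion.** The users-only difference in medians with its CI can be biased in either direction and should not be the only tabulated duration contrast for ventilation/ECMO, or for non-invasive ventilation/high-flow in scores 4 and 5. The mechanism follows from how new use is defined. The range of 0 to about 8 days rests wholly on the assumed mix of episode lengths and the assumed preventive effect.

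A reader might infer that the SAP restricts all duration endpoints to users, or that interferon is set up to look harmful. The documents support neither. The note is written for Table 33 and reaches the other tables only through the shared layout; SAP 8.2.6 and 8.2.8, which analyze new use, lend that reading some support. The body text has no such limit. The on-oxygen-at-baseline block and Tables 34 and 37 are not affected. These are secondary summaries without multiplicity adjustment (SAP 6.8), and the shell has no p-value column. The primary and key secondary results do not change. This is an inexpensive improvement to a secondary analysis.

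**What to change.** 1. In Tables 33, 35, 36 and 38 to 41, add a between-arm contrast over all patients in the stratum not on that support at baseline, with 0 days for non-users and the SAP's 28 days for deaths. Use a mean difference with CI, or a rank test. Adding non-users while keeping medians would often give 0 v 0.
2. Keep the users-only medians and quartiles as a description of duration of new use, without a between-arm difference or CI.
3. Align the programming note with SAP 8.2.3 to 8.2.8, and state which tables it governs and whether non-users count as 0.

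No new data are needed, only SAP wording and table programming. The downside is that the all-patient measure is driven partly by mortality and incidence, so it should be shown beside those results.

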1.2 Schedule of Assessments

Table 1. Schedule of Assessments (SOA)

	Screen	Baseline	Study Intervention Period	Follow-up Visits		
Day +/- Window	-1 or 1	1	Daily until hospital discharge	15⁷ ± 2	22⁷ ± 3	29⁷ + 6
ELIGIBILITY						
Informed consent	X					
Demographics & Medical Hx	X					
Review SARS-CoV-2 results	X					
STUDY INTERVENTION						
Randomization		X				
Administration of investigational agent			
 • Remdesivir daily infusion for 5-10 days or until discharge. • Interferon beta-1a or placebo SQ injection on Days 1, 3, 5, and 7, or until discharge. 			
STUDY PROCEDURES						
Targeted physical exam		X				
Vital signs including SpO ₂ ¹		X ⁴	Daily until discharge ⁸	X ⁹		X ⁹
Clinical data collection ²		X ⁴	Daily until discharge ⁸	X ⁹	X ⁹	X ⁹
Adverse event evaluation		X ⁴	Daily until discharge ⁸	X ⁹	X ⁹	X ⁹
Concomitant medication review	X	X	From Day -7 to Day 29			
SAFETY LABORATORY						
Safety hematology, chemistry and liver tests	X ³	X ^{4,5,6,7}	Day 3, 5, 8, 11 (all ± 1 day) if hospitalized ^{6,7}	X ⁹		X ⁹
Pregnancy test for females of childbearing potential	X ³					
RESEARCH LABORATORY FOR ALL SUBJECTS						
Blood for plasma to test by PCR for SARS-CoV-2 and cytokines/inflammatory markers		X ⁴	Day 3, 5, 8, 11 (all ± 1 day) if hospitalized			X ⁹

Oropharyngeal swab ¹⁰		X ⁴	Day 3, 5, 8, 11 (all ± 1 day) if hospitalized	X ⁹		X ⁹
Blood for serum (secondary research)		X ⁴	Day 3, 5, 8, 11 (all ± 1 day) if hospitalized	X ⁹		X ⁹
ONLY FOR SUBJECTS CONSENTING FOR GENETIC RESEARCH						
Blood for RNA for transcriptomic analysis (in PAXgene tube)		X ⁴	Day 3, 8 (all ± 1 day) if hospitalized	X ^{9, 11}		X ⁹
Blood for PBMC to T cells/innate cells and epigenetics (in CPT) ¹²		X ^{4,12}	Day 8 (all ± 1 day) if hospitalized ¹²	X ^{9, 11, 12}		X ^{9, 12}

Notes:

¹Vital signs include temperature, systolic blood pressure, heart rate, respiratory rate, O₂ saturation and level of consciousness. Vital signs collected as part of standard care may be used.

²Refer to [Section 8.1.2](#) of the protocol for details of clinical data to be collected including ordinal score, NEWS, oxygen requirement, mechanical ventilator requirement, etc.

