³Screening laboratory tests include: white blood cell (WBC) count, platelet count, ALT, AST, and creatinine (and calculate an estimated glomerular filtration rate (eGFR) the formula used is determined by the sites, but should be consistent throughout the study), and pregnancy test. Laboratory tests performed in the 48 hours prior to enrollment will be accepted for determination of eligibility. See [Section 8.1.1](#) for more information about pregnancy tests in post-partum women.

⁴Baseline assessments should be performed prior to first study product administration. Results of Day 1 (baseline) laboratory assessment do not need to be reviewed to determine if initial study product should be given.

⁵Laboratory tests performed as part of routine clinical care in the 36 hours prior to first dose will be accepted for the baseline safety laboratory tests. Baseline may be the same as the screening laboratory tests.

⁶Safety laboratory tests include WBC count, differential, hemoglobin, platelet count, creatinine, total bilirubin, ALT, AST, INR, d-dimer, and C-reactive protein (CRP). Note: D-dimer and CRP values may predict severity and support assessment of outcomes and unlike other safety laboratory values, D-dimer and CRP should not be graded.

⁷Any laboratory tests performed as part of routine clinical care within the specified visit window can be used for safety laboratory testing.

⁸Daily until hospital discharge or end of study, whichever comes first. See [Section 8.1.2.1](#) for more information about doing an ordinal scale assessment on the day after hospital discharge and on the day after a subject dies.

⁹In-person visits are preferred but recognizing quarantine and other factors may limit the subject's ability to return to the site for the visit. In this case, the visit may be performed by phone call, home visit or remote telehealth procedure as per institutional standards. If subject is still hospitalized during the follow-up period, they should get Day 15, 22 and 29 assessments along with the daily clinical data collection.

- If still hospitalized at Day 15 and 29 or returns to the site for an in-person visit or home visit: collect clinical data, vital signs, safety laboratory tests, and research laboratory samples (OP swab and serum only) as able.
- If phone call or remote telehealth visit only on Days 15 and 29 and all Day 22 visits: assess adverse events, clinical status (ordinal scale), readmission to a hospital, and mortality only.

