6. GENERAL STATISTICAL CONSIDERATIONS

6.1. General Principles

This is a double-blind, placebo controlled randomized trial with a two-sided type I error rate of 0.05. Secondary hypotheses have been ordered according to relative importance. These will be described according to the appropriate summary statistics, e.g.:

- Percentages/proportions/odds ratios for categorical data. For tabular summaries of percentages/proportions, the denominator (e.g. number of subjects with non-missing data) will be displayed.
- Means, median, and range for continuous data, median for time-to-event data.

Confidence intervals will be generated; for the primary analysis, the confidence level will take into account the group-sequential design of the trial (see Section 6.6 and Section 8.1) whereas 95% confidence intervals will be generated for secondary and exploratory outcomes. For hazard ratio and odds ratio estimates, Wald confidence intervals will be used. For other efficacy outcomes (e.g. proportions), Wilson or Score confidence intervals will be used. For safety outcomes, exact (e.g., Clopper-Pearson) confidence intervals will be used.

When calculating treatment effects (e.g., differences, hazard ratios, odds ratios) and when using treatment arm as a covariate in regression modeling, the placebo + remdesivir arm will be used as the reference group. For regression modeling that uses strata variables defined in Section 6.4, the first stratum listed for each variable in that section will be used as the reference group.

For the final time-to-event analyses, the following SAS pseudocode will be used to perform stratified analyses to generate stratum-specific median time to event estimates and confidence intervals, stratum-specific Kaplan-Meier curves, and to perform the log-rank test. For any unstratified analyses, code can be used after the removal of the `strata ... ;` line.

```
proc lifetest data=dataset plots=(s);
  time TimeVariable * CensorVariable(1);
  strata StrataVariable;
  test TreatmentVariable;
run;
```

Note that the interim efficacy analyses will be performed using R. For all interim and final analyses, the software used will calculate the log rank statistic using the formula in Section 8.1.1.

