6.3.2. Modified Intention-to-Treat (mITT) and As Treated Populations

The modified intention-to-treat (mITT) population includes all subjects who were randomized. mITT subjects will be classified by their randomized treatment assignment and their baseline ordinal score, which is not necessarily equivalent to the disease severity stratum to which the subject randomized at enrollment.

The As Treated population includes all randomized subjects who received the interferon beta-1a/placebo study product, even if only one dose was administered.

For As Treated analyses of efficacy outcomes, subjects will be classified by their actual treatment assignment and their baseline ordinal score, unless otherwise specified in the table or figure shell. Note that if no subjects are administered the incorrect treatment and all subjects receive at least one dose of interferon beta-1a/placebo, the As Treated efficacy analysis will not be performed as they will be identical to the mITT analyses.

For As Treated analyses of safety outcomes, concomitant medications, and medical history, subjects will be classified by their actual treatment assignment and baseline ordinal score.

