9.6. Clinical Laboratory Evaluations

Clinical safety laboratory adverse events are collected Day 1, 3, 5, 8, 11 and Day 15 and 29 if able to return to clinic or still hospitalized. Parameters evaluated include white blood cell count, absolute neutrophil count, eGFR, platelet count, hemoglobin concentration, creatinine, glucose, total bilirubin, ALT, AST, INR, d-dimer, and CRP. Laboratory safety parameters will be graded according to the Division of AIDS (DAIDS) Table for Grading the Severity of Adult and Pediatric Adverse Events, version 2.1 (July 2017). For sites that do not report an upper (lower) limit for the value of a laboratory parameter, the median of the reported upper (lower) limits across the other sites will be used.

The distribution of Grade 3 and 4 chemistry and hematology laboratory results by maximum severity, time point, disease severity and treatment group will be presented ([Table 92](#)).

Treatment-emergent laboratory abnormalities will be summarized by parameter and grade ([Table 94](#)).

Descriptive statistics including mean, median, standard deviation, maximum, and minimum values and change from baseline by time point, for all and each chemistry and hematology laboratory parameter will be summarized by disease severity and treatment arm ([Table 96](#)). Changes in chemistry and hematology laboratory values will be presented in line graphs over time with median, Q1 and Q3 plotted by disease severity and treatment arm ([Figure 49](#)).

Listings will provide a complete listing of individual chemistry and hematology laboratory results with applicable reference ranges ([Listing 22](#)).

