n = Number of subjects who died or experienced SAEs or Grade 3 or 4 AEs.
HR is the ratio of the hazard of Death/SAE/AE of Grade 3 or 4 in each treatment group estimated from the Cox model. The ratio is Interferon beta-1a + RDV to Placebo + RDV.
HR for the 'Any Baseline Ordinal Score' and 'Any Baseline Ordinal Score (4 or 5)' group is the hazard ratio from the stratified Cox Model.

Table 92: Abnormal Laboratory Results of Grade 3 or 4 by Parameter, Maximum Severity, Time Point, and Treatment Group – As Treated Population, Baseline Ordinal Score of 4 or 5

Laboratory Parameter	Time Point	Treatment Group	N	Severe/ Grade 3		Life Threatening/ Grade 4		Severe/Grade 3 or Life Threatening/Grade 4	
				n	%	n	%	n	%
Any Parameter	Baseline	Interferon + RDV	x	x	x	x	x	x	x
		Placebo + RDV	x	x	X	x	x	x	x
	Day 3	Interferon + RDV	x	x	X	x	x	x	x
		Placebo + RDV	x	x	X	x	x	x	x
	Day 5	Interferon + RDV	x	x	X	x	x	x	x
		Placebo + RDV	x	x	X	x	x	x	x
	Day 8	Interferon + RDV	x	x	X	x	x	x	x
		Placebo + RDV	x	x	X	x	x	x	x
	Day 11	Interferon + RDV	x	x	X	x	x	x	x
		Placebo + RDV	x	x	X	x	x	x	x
	Day 15	Interferon + RDV	x	x	X	x	x	x	x
		Placebo + RDV	x	x	X	x	x	x	x
	Day 29	Interferon + RDV	x	x	X	x	x	x	x
		Placebo + RDV	x	x	X	x	x	x	x
	Maximum Severity Post Baseline		Interferon + RDV	x	x	X	x	x	x
			Placebo + RDV	x	x	X	x	x	x

Each parameter will be summarized individually similar to the above...

The “Max Post Baseline” rows indicate the maximum severity experienced by each subject at any time point post baseline, including unscheduled assessments and assessments beyond Day 29.
N = Number of subjects in the As Treated Population

Programming Note: D-dimer and CRP results are not included in this table. Include all lab parameters that are being graded in this table.

Table with similar format:

Table 93: Abnormal Laboratory Results of Grade 3 or 4 by Parameter, Maximum Severity, Time Point, and Treatment Group – As Treated Population, Baseline Ordinal Score of 6

Table 94: Treatment-Emergent Laboratory Abnormalities - As Treated Population, Baseline Ordinal Score of 4 or 5

Laboratory Parameter	Grade	Interferon beta-1a + RDV (N=X)			Placebo + RDV (N=X)		
		N	n	%	N	n	%
Any Parameter	1	x	x	x	x	x	x
	2	x	x	X	x	x	x
	3	x	x	X	x	x	x
	4	x	x	X	x	x	x
	Any Grade	x	x	X	x	x	x

Continue for all graded parameters

N = Number of subjects in the As Treated Population with any post-baseline data available for the specified Lab Parameter.

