n = Number of subjects in the As Treated Population with treatment emergent abnormalities for the specified Lab Parameter.
A treatment emergent laboratory abnormality is defined as a post-baseline abnormal value with a severity grade greater than at baseline.

Table with similar format:

Table 95: Treatment-Emergent Laboratory Abnormalities - As Treated Population, Baseline Ordinal Score of 6

Table 96: Summary Statistics of Laboratory Results by Parameter, Study Visit Day, and Treatment Group – As Treated Population, Baseline Ordinal Score of 4 or 5

Laboratory Parameter	Study Visit Day	Treatment Group	Absolute					Change from Baseline				
			N	Mean	95% CI	Median	Min, Max	N	Mean	95% CI	Median	Min, Max
Parameter 1	Baseline	Interferon + RDV	x	xx.x	xx.x, xx.x	xx.x	xx.x, xx.x	---	---	---	---	---
		Placebo + RDV	x	xx.x	xx.x, xx.x	xx.x	xx.x, xx.x	---	---	---	---	---
	Day 3	Interferon + RDV	x	xx.x	xx.x, xx.x	xx.x	xx.x, xx.x	x	xx.x	xx.x, xx.x	xx.x	xx.x, xx.x
		Placebo + RDV	x	xx.x	xx.x, xx.x	xx.x	xx.x, xx.x	x	xx.x	xx.x, xx.x	xx.x	xx.x, xx.x
	Day 5	Interferon + RDV	x	xx.x	xx.x, xx.x	xx.x	xx.x, xx.x	x	xx.x	xx.x, xx.x	xx.x	xx.x, xx.x
		Placebo + RDV	x	xx.x	xx.x, xx.x	xx.x	xx.x, xx.x	x	xx.x	xx.x, xx.x	xx.x	xx.x, xx.x
	Day 8	Interferon + RDV	x	xx.x	xx.x, xx.x	xx.x	xx.x, xx.x	x	xx.x	xx.x, xx.x	xx.x	xx.x, xx.x
		Placebo + RDV	x	xx.x	xx.x, xx.x	xx.x	xx.x, xx.x	x	xx.x	xx.x, xx.x	xx.x	xx.x, xx.x
	Day 11	Interferon + RDV	x	xx.x	xx.x, xx.x	xx.x	xx.x, xx.x	x	xx.x	xx.x, xx.x	xx.x	xx.x, xx.x
		Placebo + RDV	x	xx.x	xx.x, xx.x	xx.x	xx.x, xx.x	x	xx.x	xx.x, xx.x	xx.x	xx.x, xx.x
	Day 15	Interferon + RDV	x	xx.x	xx.x, xx.x	xx.x	xx.x, xx.x	x	xx.x	xx.x, xx.x	xx.x	xx.x, xx.x
		Placebo + RDV	x	xx.x	xx.x, xx.x	xx.x	xx.x, xx.x	x	xx.x	xx.x, xx.x	xx.x	xx.x, xx.x
	Day 29	Interferon + RDV	x	xx.x	xx.x, xx.x	xx.x	xx.x, xx.x	x	xx.x	xx.x, xx.x	xx.x	xx.x, xx.x
		Placebo + RDV	x	xx.x	xx.x, xx.x	xx.x	xx.x, xx.x	x	xx.x	xx.x, xx.x	xx.x	xx.x, xx.x
Continue for all parameters...												
N = Number of subjects in the As Treated Population with laboratory data available for the parameter at the specified study visit.												

Programming Note: Include all lab parameters in this table except d-dimer and CRP.

Table with similar format:

Table 97: Summary Statistics of Laboratory Results by Parameter, Study Visit Day, and Treatment Group – As Treated Population, Baseline Ordinal Score of 6

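### Tables 92 and 93 divide by-visit Grade 3/4 laboratory counts by the whole As Treated population, although most post-baseline bloods are drawn only from inpatients

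*SAP*

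**What the plan says.** SAP section 9.6 says that Grade 3 and 4 chemistry and hematology results "by maximum severity, time point, disease severity and treatment group will be presented". It names no denominator. The shell for Table 92 (baseline score 4 or 5; Table 93 repeats it for score 6) has rows for Baseline, Days 3, 5, 8, 11, 15 and 29, and maximum severity post baseline. Its footnote reads "N = Number of subjects in the As Treated Population", with no condition that a result exists.

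That population does not shrink over time. SAP section 6.3.2: "The As Treated population includes all randomized subjects who received the interferon beta-1a/placebo study product, even if only one dose was administered".

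Sampling does shrink. The schedule in Protocol Appendix C section 1.2 sets safety bloods at "Day 3, 5, 8, 11 (all ± 1 day) if hospitalized". For the later visits its note says "If still hospitalized at Day 15 and 29 or returns to the site for an in-person visit or home visit", laboratory samples are collected as able. Phone and telehealth visits collect none.

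The neighbouring laboratory tables in SAP Appendix 1 are defined differently:

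- Table 94: "N = Number of subjects in the As Treated Population with any post-baseline data available for the specified Lab Parameter".
- Table 96, also by visit: "N = Number of subjects in the As Treated Population with laboratory data available for the parameter at the specified study visit".

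SAP section 6.1 says that for summaries of percentages "the denominator (e.g. number of subjects with non-missing data) will be displayed". Table 3 (disposition) limits its denominators on Days 3, 5, 8 and 11 to subjects who are hospitalized and in the study.

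**The concern.** A program that follows the Table 92 footnote puts every discharged, unsampled subject in the denominator as having no Grade 3 or 4 result. The percentage then mixes two quantities: how many subjects were tested, and how often those tested had a severe result. A reader could see toxicity fading over the visits when what faded was sampling.

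Tables 92 and 93 are the only planned tables of Grade 3/4 laboratory percentages by visit. Protocol Appendix C section 2.2.3.1 names transaminase elevation and low blood counts among the risks of interferon beta-1a and relies on laboratory monitoring to manage them, so these rows will be read closely.

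**Working it through.** The plan states no figure for this table, so there is none to reproduce.

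**Algebra.** For one arm at one visit, let c be the share of the As Treated arm with a result, r the Grade 3/4 rate among those tested, and q the unknown rate among those not tested.

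- Printed under the footnote: c × r.
- Printed with a data-available denominator: r.
- Rate in all treated subjects: c × r + (1 − c) × q.

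The footnote gives the all-subject rate only if q = 0. The data-available denominator gives it only if q = r. Otherwise neither does.

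**Size of the dilution.** With r = 10%, the table prints 9% at c = 0.90, 7.5% at 0.75, 5% at 0.50 and 2.5% at 0.25.

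**Illustration by visit.** The documents give no discharge times, so these are assumptions: exponential time to discharge from Day 1 with median m of 5, 8 or 10 days. Then c on Day d is 0.5^((d − 1)/m). Each cell shows c, then the printed percentage if r = 10%.

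| Visit | m = 5 | m = 8 | m = 10 |
|---|---|---|---|
| Day 3 | 0.76, 7.6% | 0.84, 8.4% | 0.87, 8.7% |
| Day 5 | 0.57, 5.7% | 0.71, 7.1% | 0.76, 7.6% |
| Day 8 | 0.38, 3.8% | 0.55, 5.5% | 0.62, 6.2% |
| Day 11 | 0.25, 2.5% | 0.42, 4.2% | 0.50, 5.0% |

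The rate among tested subjects is 10% in every cell. The fall down each column is sampling alone. Days 15 and 29 are not modelled: in-person visits are preferred then and home visits also collect bloods, so coverage may rise again.

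**Between arms.** If r is equal in both arms, the ratio of printed percentages is the ratio of coverages.

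- Equal coverage: ratio 1, no distortion.
- Coverage 40% against 60%, r = 10%: 4% against 6%, ratio 0.67.
- Discharge rate ratio of 1.25 (borrowed from the recovery ratio in SAP section 5; an assumption for discharge), Day 11, r = 10%, faster-discharged arm first: 1.8% against 2.5% (m = 5, ratio 0.71), 3.4% against 4.2% (m = 8, ratio 0.81), 4.2% against 5.0% (m = 10, ratio 0.84).

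At low rates this would often not show. SAP section 13 rounds percentages to whole numbers. With r = 4% on Day 11, the same model gives 2.0% and 1.7% (m = 10), which print as 2 and 2, or 1.0% and 0.7% (m = 5), which print as 1 and 1.

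**The opposite case.** Suppose q = 0, the all-subject rate is 5% in both arms, and coverage is 40% against 60%. The footnote prints 5% in both. A data-available denominator prints 0.05/0.40 = 12.5% against 0.05/0.60 = 8.3%, so the faster-discharged arm looks worse with no true difference among all subjects.

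**Rows not at issue.** Nearly everyone has a Baseline sample. The Maximum Severity row uses any post-baseline result, including unscheduled ones, so a subject needs only one sample to count.

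**The case against.** The footnote may be a drafting slip. The shell has an N cell in every row, which a fixed population would not need. The wording also leaves out the arm and the baseline-score restriction. Other shells carry clear carry-over errors: renal Table 65 has a row for hepatic events, and mortality Table 82 defines n as recovered subjects. Section 6.1 offers non-missing data as its example denominator. This is plausible and lowers the stakes, but an example in a general section does not override an explicit footnote, and nothing else tells the programmer which N to use.

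The information is partly available elsewhere. Table 94 grades abnormalities among subjects with data, Table 96 summarises values by visit among subjects with data, Listing 22 gives every graded result, and Table 3 counts safety blood draws by visit and arm. Table 92 is descriptive and drives no decision rule. All of this stands. Table 3, however, uses the mITT population and an inpatient denominator on Days 3 to 11, so coverage of the As Treated arm has to be pieced together.

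A reader might infer something stronger: that the table understates toxicity and makes the faster-discharged arm look safer. The documents do not support that. It needs coverage to differ by arm and untested subjects to have the same rate as tested ones. The documents establish neither, nor do they say which arm would leave hospital sooner. Inpatients are probably the sicker remainder, and if discharged subjects are free of severe abnormalities, the footnote percentage is the correct all-subject prevalence.

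The illustration is also rough. The 10-day median is the ACTT-1 time to recovery on remdesivir, and recovery can occur in hospital. Anticipated discharge within 72 hours is an exclusion, so the Day 3 dilution is probably smaller than modelled.

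**Conclusion.** The inconsistency is real and should be corrected. As written, the Day 3 to Day 29 percentages in Tables 92 and 93 equal coverage times the rate among those tested, so they move with sampling and cannot be set beside Tables 94 and 96. That result is algebra and needs no assumption about discharge. Its size does: in the illustration a 10% rate among tested subjects prints as 2.5% to 5.0% on Day 11 for assumed median discharge times of 5 to 10 days.

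A between-arm distortion is possible but conditional. It requires unequal coverage, and its size and direction depend on discharge times and on the unknown rate in untested subjects. No direction should be claimed. The primary analysis is untouched; this is a fault in a safety display.

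**What to change.** Replace the footnote in Tables 92 and 93 with:

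*N = number of subjects in the As Treated Population, in the specified treatment arm and baseline ordinal score group, with a result for the parameter at the specified time point. For Any Parameter rows: with at least one graded parameter result at that time point. For Maximum Severity Post Baseline rows: with any post-baseline result.*

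Also print the As Treated arm size for that baseline group, so that coverage by arm is visible and a reader can form either percentage from n. Add a note that by-visit percentages describe sampled subjects only, who on Days 3 to 11 are inpatients. The coverage figure and the note are needed because the new denominator describes a selected group.

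The cost is one footnote shared by two tables, one denominator in the table program, and one extra column or header entry. No new data are needed.
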